Appendix 6. Cohort Dosing Schedule

- Up to 8 subjects for Part A and up to 16 subjects total for Parts B/C may be added as part of expansion of an existing cohort or cohorts if further data is required. The allocation of the floater subjects in Parts B/C are not required to be distributed evenly. The total combined n for Parts B/C will not exceed 48 subjects.
- The doses designated in Parts B/C schedule are indicative of a single dose of VIR-2218 or placebo; subjects will receive up to 2 doses total.

14.	HANDLING OF MISSING DATA	35
15.	CHANGES TO THE PLANNED ANALYSIS	36
16.	INTERIM AND FINAL ANALYSIS	37
16.1	Interim Analysis 1	37
16.2	Final Analysis (End of Study)	38
17.	SOFTWARE	39
18.	TABLES, Listings and figures	40
19.	REFERENCES	41

List of Abbreviations

Abbreviation	Description
AE	Adverse Event
ALP	Alkaline Phosphatase
ALT	Alanine Aminotransferase
Anti-HBe	Hepatitis B extracellular antibody
AST	Aspartate Aminotransferase
ATC	Anatomical Therapeutic Chemical
BMI	Body Mass Index
BUN	Blood urea nitrogen
cccDNA	Covalently Closed Circular DNA
C-G	Cockcroft-Gault
CHB	Chronic Hepatitis B
CS	Clinically Significant
CSR	Clinical Study Report
CV	Coefficient of Variation
DBP	Diastolic Blood Pressure
ECG	Electrocardiogram
eCRF	Electronic Case Report Form
FU	Follow-up
GCP	Good Clinical Practice
GGT	Gamma-Glutamyl Transferase
CCI	
HBV	Hepatitis B Virus
HBeAg	Hepatitis B e-Antigen
HBsAg	Hepatitis B Surface Antigen
HCV	Hepatitis C Virus
HIV	Human Immunodeficiency Virus
INR	International Normalized Ratio
IVRS/IWRS	Interactive Voice/Web Response System
LDH	Lactic Acid Dehydrogenase
LLOQ	Lower limit of quantification
LOD	Limit of Detection
MAD	Multiple Ascending Dose
MedDRA	Medical Dictionary for Regulatory Activities
N/A	Not Applicable
NCS	Not Clinically Significant
NK	Not Known
NRTI	Nucleos(t)ide Reverse Transcriptase Inhibitor
PD	Pharmacodynamic
PI	Principal Investigator
PK	Pharmacokinetic

Abbreviation	Description
PT	Preferred Term
Q1	First Quartile
Q3	Third Quartile
SAE	Serious Adverse Event
SAP	Statistical Analysis Plan
SAD	Single Ascending Dose
SBP	Systolic Blood Pressure
SD	Standard Deviation
S.I.	International System of Units
SRC	Safety Review Committee
SOC	System Organ Class
SOP	Standard Operating Procedure
SUSAR	Suspected Unexpected Serious Adverse Reactions
TEAE	Treatment Emergent Adverse Event
TSH	Thyroid Stimulating Hormone
ULOQ	Upper limit of quantification
WHO-DD	World Health Organization Drug Dictionary

1. INTRODUCTION

The following Statistical Analysis Plan (SAP) provides the outline for the statistical analysis of the data collected from the VIR-2218-1001 study [REDACTED]

The planned analyses identified in this SAP may be included in clinical study reports (CSRs), regulatory submissions, or future manuscripts. Also, post hoc exploratory analyses not necessarily identified in this SAP may be performed to further examine study data. Any post hoc, or unplanned, exploratory analyses performed will be clearly identified as such in the final CSR.

2. PROJECT OVERVIEW

2.1 Study Design

Part A to C:

[figure not shown]
This is a randomized, double-blind, placebo-controlled study of VIR-2218 administered subcutaneously to healthy adult subjects and non-cirrhotic adult subjects with chronic hepatitis B virus (HBV) infection who are on nucleos(t)ide reverse transcriptase inhibitor (NRTI) therapy. The study is designed to evaluate the safety, tolerability, Pharmacokinetic (PK), and antiviral activity of VIR-2218. Part A is planned to be conducted at 1 clinical investigative site; Parts B and C are planned to be conducted at multiple clinical investigative sites in the Asia-Pacific region. The study designs for Part A, phase 1 single ascending dose (SAD) and Part B/C, phase 2 multiple ascending dose (MAD) are presented in Figure 1 and Figure 2, respectively.

Figure 1: **SAD Study Design for Part A**

^aSubject discharge will occur after all assessments are completed on Day 2.

Figure 2: **MAD Study Design for Part B/C**

^aAdditional Hepatitis B Surface Antigen (HBsAg) monitoring is required for subjects with HBsAg levels with a > 10% decrease from the Day 1 predose level at the Week 16 visit. Visits will occur every 4 weeks starting at Week 20 up to Week 48 or until the HBsAg level returns to > 90% of the Day 1 predose level. Additional HBsAg monitoring may be discontinued at the Sponsor's discretion based on emerging data.

Part A Single Ascending Dose Phase in Healthy Adult Subjects

Healthy adult subjects will be enrolled in 1 of 4 planned ascending dose cohorts. At the start of each cohort, 2 sentinel subjects will be randomized 1:1 to VIR 2218 or placebo. These subjects will be dosed concurrently and monitored for 24 hours; if the investigator has no safety concerns, the remainder of the subjects in the same cohort will be dosed. Vital signs, symptom-directed physical examination(s), and AEs will be reviewed by the investigator prior to dosing any additional subjects. The remaining subjects will be randomized 5:1 to receive a single dose of VIR 2218 or placebo.

Subject screening will occur no more than 4 weeks prior to the Day 1 visit. Eligible subjects will be confined to the clinical investigative site on Day -1 to determine continued eligibility and for predose assessments. Subjects in each cohort will be randomized to receive VIR-

2218 or placebo within 48 hours prior to study drug administration. Subjects will receive a single dose of study drug on Day 1 (VIR 2218 or placebo). Subjects will be discharged from the clinical investigative site after all assessments are completed on Day 2.

Subjects will return to the clinical investigative site on an outpatient basis for safety, tolerability, and PK monitoring at specified timepoints through the last Post-dose Follow-up Visit (Week 12).

Based on review of the accumulated, available data in Part A, the SRC may recommend dosing of 2 optional cohorts. In addition to the optional cohorts, up to 8 “floater” subjects for Part A may be added to any cohort, as determined and approved by the SRC.

Fasting is not required for any study procedure/assessment.

Part B/C Multiple Ascending Dose Phase in Non-Cirrhotic Adult Subjects with Chronic HBV Infection on Nucleoside/Nucleotide Therapy

Non-cirrhotic adult subjects with chronic HBV infection on NRTI therapy for ≥ 6 months will be enrolled in the Part B/C cohorts. Part B will enroll HBeAg negative subjects. Part C will enroll HBeAg positive subjects. Eligible subjects should have HBV DNA < 90 IU/mL. Each cohort in Part B/C will be composed of 4 subjects randomized 3:1 to VIR 2218 or placebo, respectively. There are 3 planned and 2 optional cohorts in Part B. There are 1 planned and 2 optional cohorts in Part C.

Subjects enrolled in Part B/C of the study will remain outpatient. Subject screening will occur no more than 4 weeks prior to the Day 1 visit. Eligible subjects will undergo further assessments on Day 1 to qualify for study drug administration on Day 1. To exclude the presence of cirrhosis, screening will include a mandatory noninvasive assessment of liver fibrosis such as a FibroScan evaluation, unless the subject has results from a FibroScan evaluation performed within 6 months prior to screening or a liver biopsy performed within 1 year prior to screening that confirms the absence of Metavir F3 fibrosis or F4 cirrhosis.

Subjects in each cohort will be randomized 3:1 to receive VIR 2218 or placebo within 48 hours prior to study drug administration on Day 1. Subjects will return to the clinical investigative site at Week 4 to receive a second dose of the same study drug administered on Day 1. The decision to administer a second dose will be made based on Week 3 laboratory values in accordance with dose suspension/stopping criteria in Section 4.84.6.

Additional blood samples for possible analyses to elucidate VIR 2218 activity and/or host responses to infection and treatment will be collected.

Subjects will return to the clinical investigative site on an outpatient basis for safety, tolerability, PK, and antiviral activity monitoring at specified timepoints through the last Post dose Follow up Visit (Week 16). Additional HBsAg monitoring is required for subjects with HBsAg levels with a $> 10\%$ decrease from the Day 1 predose level at the Week 16 visit. Visits will occur every 4 weeks starting at Week 20 up to Week 48 or until the HBsAg level returns to $> 90\%$ of the Day 1 predose level. Additional HBsAg monitoring may be discontinued at the Sponsor’s discretion based on emerging data.

Based on review of the accumulated, available data in Parts A, B, and C, the SRC may recommend dosing of optional cohorts following the same stratification. In addition to the optional cohorts, a combined total of up to 16 “floater” subjects for Part B/C may be added to any cohort, as determined and approved by the SRC.

Fasting is not required for any study procedure/assessment.

Safety Review Committee

In Parts A – C, a SRC will perform ongoing reviews of safety, tolerability, and available study data collected throughout the study with the primary purpose of protecting the safety of subjects participating in this clinical study. The SRC will be governed by an SRC Charter that will be finalized prior to screening the first subject.

The SRC will undertake safety data review prior to initiation of dosing a new cohort in Parts A, B, and C of the study in accordance with the SRC Charter. Ad hoc SRC meetings may take place as needed, e.g., for a significant safety event such as a subject or cohort stopping criterion being reached (Section 4.8 of the protocol). In Parts D - F of the study, the SRC may meet ad hoc, and/or in the event an unexpected safety concern is identified.

Decisions to suspend dosing or discontinue individual subjects from study drug will be made according to predetermined stopping rules (Section 4.8 of the protocol). Additionally, the SRC may recommend discontinuation of the study to the Sponsor. The SRC membership composition is described in detail in the SRC Charter.

2.2 Objectives

2.2.1 Primary objective

The primary objectives of this study are:

- Part A: To evaluate the safety and tolerability of a single dose of VIR-2218 in healthy adult subjects.
- Part B/C: To evaluate the safety and tolerability of multiple doses of VIR-2218 in non-cirrhotic subjects with HBeAg-negative (Part B) and HBeAg-positive (Part C) chronic HBV infection on NRTI therapy.

2.2.2 Secondary objectives

The secondary objectives of this study are:

- Part A:
 - To characterize the PK of VIR-2218 in healthy adult subjects.
- Part B/C:
 - To characterize the PK of VIR-2218 in non-cirrhotic subjects with chronic HBV infection on NRTI therapy.
 - To assess the antiviral activity of VIR-2218 in non-cirrhotic subjects with chronic HBV infection on NRTI therapy.

CCI

2.3 Endpoints

2.3.1 Primary endpoints

- Part A/B/C:
 - Incidence of AEs
 - Clinical assessments including but not limited to laboratory test results

2.3.2 Secondary endpoints

- Part A:
 - PK parameters of VIR-2218 and possible metabolites (may include, but not limited to plasma: maximum concentration, time to reach maximum concentration, area under the concentration versus time curve [to last measurable timepoint and to infinity], percent of area extrapolated, apparent terminal elimination half-life, clearance, and volume of distribution; urine: fraction eliminated in the urine and renal clearance).

- Part B/C:
 - PK parameters of VIR-2218 and possible metabolites (may include, but not limited to plasma: maximum concentration, time to reach maximum concentration, area under the concentration versus time curve [to the last measurable timepoint and to infinity], apparent terminal elimination half-life, clearance, and volume of distribution).
 - Maximum reduction of serum HBsAg from Day 1 until Week 16.
 - Number of subjects with serum HBsAg loss up to all timepoints.
 - Number of subjects with sustained serum HBsAg loss for ≥ 6 months.
 - Number of subjects with anti-HBs seroconversion at any timepoint.
 - For HBeAg-positive subjects (Part C only): number of subjects with HBeAg loss and/or anti-HBe seroconversion at any timepoint.

CCI

2.4 Sample Size

No formal sample size calculation was conducted. Up to 104 subjects (up to 56 healthy subjects and up to 48 subjects with chronic HBV infection) are planned to complete the study. The 209 subjects includes “floater” subjects (up to 8 healthy subjects in Part A and up to 16 subjects with chronic HBV infection in Part B and C) that may be added as part of expansion of an existing cohort or cohorts based on SRC recommendations if further data are necessary.

2.5 Randomization

An Interactive Web Response System (IWRS) will be employed to manage subject randomization and treatment assignments.

Four dose-level cohorts are planned for Part A: 50 mg, 100 mg, 200 mg, and 400 mg. Two sentinel subjects will be randomized 1:1 to VIR-2218 or placebo. These subjects will be dosed concurrently and monitored for 24 hours; if the investigator has no safety concerns, the remainder of the subjects in the same cohort will be dosed. The remaining subjects will be randomized 5:1 to VIR-2218 or placebo.

Two optional cohorts in Part A may be added following the same stratification, including sentinel dosing, up to a maximum dose of 900 mg. In addition to the optional cohorts, a total of 8 “floater” subjects may be added to expand any cohort in Part A. “Floater” subjects are to be added in increments of 4 and randomized 3:1 to VIR-2218 or placebo.

Three dose-level cohorts are planned for Part B: 50 mg, 100 mg, and 200 mg. One dose-level cohort is planned for Part C: 200 mg. Each cohort in Part B/C will be randomized 3:1 to VIR-2218 or placebo.

Two optional cohorts in Part B and 2 optional cohorts in Part C may be added following the same stratification, up to a maximum dose of 450 mg per dose (900 mg cumulative dose). In addition to the optional cohorts, a pool of 16 “floater” subjects may be added to expand any cohort in Part B and/or C if further data are needed. “Floater” subjects are to be added in increments of 4 (3:1) to maintain the randomization ratio.

In Parts A-C, blinding of study treatment will be managed by the clinical investigative site’s pharmacy in accordance with the Pharmacy Manual. In the event of a medical emergency where breaking the blind is required to provide medical care to the subject, the investigator may obtain treatment assignment for that subject. IWRS should be used as the primary method of breaking the blind. If IWRS cannot be accessed, the investigator should contact the Sponsor medical monitor to break the blind. Treatment assignment should remain blinded unless that knowledge is necessary to guide subject emergency medical care. The investigator is requested to contact the Sponsor medical monitor promptly in case of any treatment unblinding.

Blinding of study treatment is critical to the integrity of this clinical trial and therefore, if a subject's treatment assignment is disclosed to the investigator, the subject will have study treatment discontinued. All subjects will be followed until study completion unless consent to do so is specifically withdrawn by the subject.

The Sponsor or designee may independently unblind cases for expedited reporting of suspected unexpected serious adverse reactions (SUSARs) as required by regulators.

3. STATISTICAL CONSIDERATIONS

Data will be handled and processed per the sponsor's representative [REDACTED] Standard Operating Procedures (SOPs), which are written based on the principles of good clinical practice (GCP).

3.1 General Considerations

All data collected on the electronic case report form (eCRF) will be presented in the data listings and will be listed and sorted by treatment arm, subject number and visit, where applicable. All summaries will be presented by treatment arm.

When reporting descriptive statistics, the following rules will apply, except for PK concentration data:

- Continuous variables: Descriptive statistics will include the number of non-missing values (n), arithmetic mean, standard deviation (SD), median, first quartile (Q1), third quartile (Q3), minimum and maximum values.

The minimum and maximum values will be displayed to the same decimal precision as the source data, the arithmetic mean, SD, median, Q1 and Q3 values will be displayed to one more decimal than the source data for the specific variable.

The appropriate precision for derived variables will be determined based on the precision of the data on which the derivations are based, and statistics will be presented in accordance with the abovementioned rules.

n will be an integer. If no subjects have data at a given time point, then only n=0 will be presented.

All data will be presented to a maximum of 3 decimal places.

- Categorical variables: Descriptive statistics will include counts and percentages per category. The denominator in all percentage calculations will be the number of subjects in the relevant analysis set with non-missing data, unless specifically stated otherwise. Percentages will be displayed to one decimal place.

Percentage change from Baseline values will be calculated and displayed to 1 decimal place in the listings. In the summaries, the mean, SD and median percentage change from Baseline values will be presented to 2 decimal places and the minimum and maximum values presented to 1 decimal place.

For categories where all subjects fulfill certain criteria, the percentage value will be displayed as 100. For categories where zero subjects fulfill certain criteria, there will be no percentage displayed. All other percentage displays will use 1 decimal place. Data listings will contain all reported and derived data.

Unless otherwise stated, the following methods will be applied:

- Repeat/unscheduled assessments: Only values collected at scheduled study visits/time points will be presented in summary tables. If a repeat assessment was performed, the result from the original assessment will be presented as the result at the specific visit/time point. All collected data will be included in the data listings. Unscheduled assessments intended as a re-test to replace missing values for scheduled visit will be used as if the results were taken on the scheduled visit for the purpose of summary table reporting.
- Assessment windows: All assessments will be included in the data listings and no visit windows will be applied to exclude assessments that were performed outside of the protocol specified procedure windows.
- Result display convention: Results will be center aligned in all summary tables and listings. Subject identifiers visit and parameter labels may be left-aligned if required.

- Date and time display conventions: The following display conventions will be applied in all outputs where dates and/or times are displayed:
 - Date only: YYYY-MM-DD
 - Date and time: YYYY-MM-DD HH:MM

If only partial information is available, unknown components of the date or time will be presented as 'NK' (not known), i.e., '2016-NK-NK'. Times will be reported in military time.

3.2 Key Definitions

The following definitions will be used:

- Baseline: The baseline value is defined as the last available valid (quantifiable continuous or categorical value), non-missing observation for each subject prior to first study drug administration. Repeat and unscheduled assessments will be included in the derivation of the baseline values. Multiple pre-dose observations taken on the same date will be averaged as baseline values.
- Change from Baseline: The change from baseline value is defined as the difference between the result collected/derived at a post-baseline visit/time point and the baseline value.

The change from baseline value at each post-baseline visit/time point will be calculated for all continuous parameters using the following formula:

$$\text{Change from Baseline Value} = \text{Result at Visit/Time Point} - \text{Baseline Value}$$

The change from baseline value will only be calculated if the specific post-baseline visit/time point result and the baseline value for the parameter are both available and will be treated as missing otherwise.

- Study day: The study day of an event is defined as the relative day of the event starting with the date of the first study drug administration (reference date) as Day 1 (there will be no Day 0).

The study day of events occurring before the first study drug administration will be calculated as:

$$\text{Study Day} = (\text{Date of Event} - \text{Date of First Study Drug Administration})$$

For events occurring on or after Day 1, study day will be calculated as:

$$\text{Study Day} = (\text{Date of Event} - \text{Date of First Study Drug Administration}) + 1$$

Study days will only be calculated for events with complete dates and will be undefined for events that are 'Ongoing' at the end of the study.

Relative days compared to an alternative reference point will be calculated similarly, but the alternative starting reference start date will be used instead of the date of the first study drug dosing.

- HBsAg loss: quantitative HBsAg < 0.05 IU/mL at two or more consecutive measurements
- HBsAg Seroconversion: anti-HBs positivity at two or more consecutive measurements
- HBeAg loss (HBeAg+ subjects only): quantitative HBeAg < 0.11 IU/mL at two or more consecutive measurements
- HBeAg Seroconversion (HBeAg+ subjects only): anti-HBe positivity at two or more consecutive measurements

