3.2. Part B/C Endpoints

The primary endpoints are:

- Incidence of AEs
- Clinical assessments including but not limited to laboratory test results

The secondary endpoints are:

- PK parameters of VIR-2218 and possible metabolites (may include, but not limited to plasma: maximum concentration, time to reach maximum concentration, area under the concentration versus time curve [to the last measurable timepoint and to infinity], apparent terminal elimination half-life, clearance, and volume of distribution)
- Maximum reduction of serum HBsAg from Day 1 until Week 16
- Number of subjects with serum HBsAg loss at any timepoint
- Number of subjects with sustained serum HBsAg loss for ≥ 6 months
- Number of subjects with anti-HBs seroconversion at any timepoint
- For HBeAg-positive subjects (Part C only): number of subjects with HBeAg loss and/or anti-HBe seroconversion at any timepoint

CCI

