Alcohol intake assessment ^g		X		X	X	X	X	X	X	X	X	X	X	X	X	X
Body weight	X															
Height and BMI	X															
Vital signs ^h	X	X	X	X	X	X	X	X	X	X	X	X	X			
Safety ECG ⁱ	X	X	X				X									
Pregnancy test ^j	X	X					X				X	X	X			
FibroScan ^k	X															
Screening viral serology ^l	X															
Laboratory assessments ^m	X	X	X	X	X	X	X	X	X	X	X	X	X	X ⁿ	X ⁿ	X ⁿ
Urinalysis ^m	X	X														

Part B/C																
Study Stage	Screening	Dosing Period						Post-dose Follow-up Period ^b						Extended Follow-up Period ^c		
Study Visit Week				W1	W2	W3	W4 ^a	W5	W6	W7	W8	W12	W16	W20	W24	
Study Visit Day ± Visit Window	D -28 to -1	D1 ^a	D2	D8 ±2	D15 ±2	D22 ±2	D29 ^a ±2	D36 ±2	D43 ±2	D50 ±2	D57 ±2	D85 ±7	D113 ±7/ET	D141 ±7	D169 ±7	Q28D ±7
Urine for drugs of abuse ^o	X															
Randomization		X														
Study drug administration ^p		X					X									
Blood samples for PK analysis ^q		X	X	X			X ^r	X								
Blood sample for HBsAg	X	X	X	X	X	X	X	X	X	X	X	X	X	X	X	X
Blood sample for anti-HBs	X										X		X		X	X ^s
Blood sample for HBeAg qualitative	X															
Blood sample for HBeAg quantitative for Part C only ^t		X					X				X	X	X		X	X ^s
Blood sample for anti-HBe for Part C only	X										X		X		X	X ^s
Blood sample for HBV DNA quantitation ^u	X	X					X				X	X	X	X	X	X ^s
CCI																

Part B/C																
Study Stage	Screening	Dosing Period						Post-dose Follow-up Period ^b						Extended Follow-up Period ^c		
Study Visit Week				W1	W2	W3	W4 ^a	W5	W6	W7	W8	W12	W16	W20	W24	
Study Visit Day ± Visit Window	D -28 to -1	D1 ^a	D2	D8 ±2	D15 ±2	D22 ±2	D29 ^a ±2	D36 ±2	D43 ±2	D50 ±2	D57 ±2	D85 ±7	D113 ±7/ET	D141 ±7	D169 ±7	Q28D ±7
CCI																
Review/Record AEs ^x	X															
Concomitant Medications	X															
NUC medication adherence	X															

AE = adverse event; ECG = electrocardiogram; ET=end of treatment; **CCI** HBeAg = hepatitis e-antigen; HBsAg = hepatitis B surface antigen; HBV = Hepatitis B Virus; NUC = nucleoside/nucleotide; PK = pharmacokinetics; MAD = multiple ascending dose

Note: When scheduled at the same timepoints, the assessments of vital signs and 12-lead ECGs must be performed first, before the physical examinations, blood sample collections, and urine collections.

^a Assessments performed predose unless otherwise specified.

^b If a subject withdraws prematurely from the study prior to their Week 16 visit, ET assessments should be performed.

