^r As a part of the Week 4 visit, subjects will return to the study center 24-hours after their initial post dose Week 4 PK sample is drawn to have a 24-hour post dose PK sample drawn.

^s Testing should occur again only at Week 36 and Week 48.

CCI

^u If a subject experiences ALT flare (as defined by ALT > 2x ULN) additional HBV DNA quantitation sample(s) may be collected

CCI

CCI

^x All AEs related to screening activities must be collected from the time of consent onwards; any other events occurring during the screening period should be reported as medical history. All SAEs must be collected from the time of consent onwards.

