13.2 Biostatistical methods

All antiviral data collected at scheduled and unscheduled visits will be included in the listings, but only results collected as scheduled visits will be included in the summary tables.

The parameter names that will be used in the outputs will comprise of the test name and the unit of measure, for example, HBsAg (IU/mL). For HBV DNA both IU/mL and copies/mL CCI will be presented. For HBV DNA, undetected and <LOQ will be imputed as 9 U mL. Parameters will be sorted within parameter class (if present) in alphabetical order within the tables and listings.

Summary for serum log₁₀ HBsAg nadir level and time to nadir will be based on all scheduled and un-scheduled post-baseline visits. Measurements will present summary statistics for the results at the baseline and each scheduled post-baseline visit for each of the parameters. In addition, summaries will be presented for the change from baseline of the antiviral measure to that assessed at baseline values at each scheduled post-baseline visit. See section 3.1 for more detail with regards continuous data representation. Categorical summaries (% of subjects) will present counts and percentages for the reported results at baseline and each post-baseline time point. Additionally, HBV DNA CCI will be summarized into TND, <LOQ, and >LOQ categories.

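### SAP 3.2 defines seroconversion without requiring a negative baseline or post-baseline samples, so a subject already antibody-positive at screening can be counted as a converter.

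*SAP*

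**What the plan says.** Protocol Section 3.2 lists among the Part B/C secondary endpoints: "Number of subjects with anti-HBs seroconversion at any timepoint". For Part C it adds HBeAg loss and/or anti-HBe seroconversion. SAP Section 13.1 repeats both.

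The operational rules are in SAP Section 3.2. For the surface antigen: "HBsAg Seroconversion: anti-HBs positivity at two or more consecutive measurements". For the e-antigen: "HBeAg Seroconversion (HBeAg+ subjects only): anti-HBe positivity at two or more consecutive measurements". SAP Sections 13.1 and 13.2 add no condition to either rule.

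The sampling times are in the Part B/C schedule, Protocol Appendix 3, in the rows "Blood sample for anti-HBs" and "Blood sample for anti-HBe for Part C only". Both are drawn at Screening, Week 8 and Week 16 (or early termination). Subjects in extended follow-up are sampled again at Week 24, and after that the footnote reads: "Testing should occur again only at Week 36 and Week 48". There is no antibody sample on Day 1.

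Protocol Sections 5.4 and 5.5 set no criterion on anti-HBs or anti-HBe.

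**The concern.** Seroconversion is a change from antibody-negative to antibody-positive. The rule as written tests only for two adjacent positives. The Screening sample is the only scheduled pre-dose antibody result, so it serves as the baseline. It is also the measurement immediately before Week 8, so a Screening and Week 8 pair satisfies the rule.

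The companion surface-antigen endpoint does not share this gap. HBsAg loss requires a value below 0.05 IU/mL, while entry requires HBsAg above 150 IU/mL, so nobody can enter already meeting it. Seroconversion has no equivalent protection from the entry criteria.

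What is at stake is a wrong count on a named secondary endpoint, tabulated by cohort where cohorts have three active subjects. A pre-existing antibody could be reported as a response in either the VIR-2218 or the placebo column.

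**Working it through.** The plan states no rate, power or sample-size figure for this endpoint, so there is nothing to reproduce. The check is to list every possible sequence of results and apply the rule literally. These are counts of possible patterns, not probabilities.

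**Inputs**
- Core antibody samples: Screening, Week 8, Week 16 (Protocol Appendix 3).
- Full schedule with extended follow-up: the same plus Weeks 24, 36 and 48.
- Rule: at least two consecutive positives (SAP 3.2).
- Cohort size in Part B/C: 4 subjects randomized 3:1, so 3 active (Protocol 4.1.2).

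**Core schedule: 2³ = 8 patterns**

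| Screening | Week 8 | Week 16 | SAP 3.2 as written | Negative baseline and two post-baseline positives |
|---|---|---|---|---|
| − | − | − | no | no |
| − | − | + | no | no |
| − | + | − | no | no |
| − | + | + | **yes** | **yes** |
| + | − | − | no | no |
| + | − | + | no | no |
| + | + | − | **yes** | no |
| + | + | + | **yes** | no |

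Three patterns qualify as written, and two of the three are screening-positive. One (+ + −) qualifies only by pairing Screening with Week 8. A lone screening positive (+ − −) does not qualify.

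**Full schedule to Week 48: 2⁶ = 64 patterns**
- As written, 43 qualify. Of these, 24 are screening-positive, and 5 of the 24 qualify only through the Screening and Week 8 pair.
- Restricting the rule to post-baseline samples alone leaves 38 qualifying, of which 19 are still screening-positive. On the core schedule, the same restriction leaves 2 qualifying, of which 1 is screening-positive. A post-baseline restriction is therefore not enough by itself.
- Adding the negative-baseline condition leaves 38 − 19 = 19 of 64 (core: 2 − 1 = 1 of 8), none of them screening-positive.

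**Effect of one misclassified subject**
- Active cohort of 3: 1/3 = 33.3 percentage points.
- Active cohort of 6, after one block of four floaters (3 active): 1/6 = 16.7 percentage points.

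**The case against.** The best defence is that the word itself implies a change from negative, and that a programmer would read it so. Protocol Section 1.1 also describes absence of detectable anti-HBs as a hallmark of chronic infection, so baseline positivity should be uncommon. SAP 13.2 provides categorical summaries at baseline and all data are listed, so a baseline-positive subject in a 4-subject cohort could be spotted. The endpoint is descriptive, with no hypothesis test and no role in sample size.

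Most of this stands as a limit on the consequence. It does not repair the definition. A key-definitions section is what the programmer codes from, the hallmark statement is background and not an entry criterion, and it says nothing about anti-HBe in Part C. A listing lets a reader trace the error, but the table would still carry it.

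A reader might also infer that the rule unfairly misses true converters, because a first positive at Week 16 cannot count in a subject who leaves then, although the endpoint is open to any timepoint. The documents do not support pressing this:
- Losing a first positive at the last sample is inherent in any confirmation rule, and a confirmed event can still occur at any timepoint.
- A subject who completes Week 16 and does not enter extended follow-up on the HBsAg rule has HBsAg at 90% or more of Day 1. Taking Day 1 as close to the entry minimum of 150 IU/mL, that is about 0.90 × 150 = 135 IU/mL or more, far from antigen loss. Subjects with a larger fall continue, and a Week 16 positive can be confirmed at Week 24 if they remain in follow-up.
- SAP 13.2 says "only results collected as scheduled visits will be included in the summary tables", but that governs what is tabulated. It does not say how a derived event is confirmed.

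**Conclusion.** The point holds for false converters. As written, SAP 3.2 counts a subject who was antibody-positive before dosing and has two adjacent positives. This applies to anti-HBs in Parts B and C and to anti-HBe in Part C. Two of the three qualifying core patterns are of this kind, and one such subject shifts a 3-subject active cohort by 33 percentage points. The conclusion rests on reading the definition literally and on the sampling times in Protocol Appendix 3.

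How many subjects are affected cannot be determined: the documents give no frequency of antibody positivity at entry, and a screening positive alone is not sufficient. A reader might multiply an assumed prevalence by the 48-subject ceiling for Part B/C. That would rest on an unsourced rate, treat the ceiling as actual enrolment, include placebo subjects and ignore the need for a second adjacent positive.

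A reader might also infer that seroconversion must require loss of the corresponding antigen. The protocol lists HBsAg loss and anti-HBs seroconversion as separate endpoints and joins the e-antigen outcomes with and/or, so the absence of that condition is consistent with the protocol. The defect is limited to the missing baseline and post-baseline conditions. It is worth correcting, but it does not affect the trial's primary safety objective.

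**What to change.** In SAP Section 3.2, define both seroconversions as antibody negative at baseline and antibody positive at two or more consecutive post-baseline measurements. State that the denominator is subjects who are antibody-negative at baseline; this has to be explicit because SAP 3.1 otherwise defaults to all subjects in the analysis set with non-missing data. List baseline-positive subjects separately.

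Optionally, flag a first positive at the last available sample as unconfirmed in the listing, so that it is visible without being counted.

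The cost is a short wording change, a denominator footnote and one listing. No new samples or visits are needed.
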